The study sample size derives from the use of the 3+3, rule-based, modified Fibonacci, dose escalation design, with 3:1 randomization to active treatment vs sham control. There will be 6 dose tiers, reflecting increasing intensity and duration of stimulation (Figure 7). The 3+3 study design (3 patients and 1 sham) with 6 dose tiers yields a sample size of at least 24 and potentially up to 48. The 3+3 design is the classical approach to dose escalation in first-in-human studies.^{47,48} While newer, adaptive designs for dose escalation trials have been developed, they are more complex and have limited advantages when major toxicities are not expected.⁴⁹ Therefore, the rule-based, 3+3 design remains the dominantly employed approach in current dose-escalation studies. We will take every step to avoid missing data by scheduling of the follow-up visits early in visit time windows and readiness to travel to the patient's location to perform needed assessments. Should any missing data occur, primary analyses will be performed using multiple imputation, with sensitivity analyses including complete case and worst possible outcome analyses.⁵⁰

E.2.2. Baseline characteristics

The demographic and baseline clinical characteristics of the study population will be delineated with standard descriptive statistics. Categorical variables describing the clinical history, examination findings, and initial treatment will be summarized by frequencies. Continuous variables such as vital signs, laboratory results, and time variables will be characterized by means, standard deviations, and 95% confidence intervals (CI). Ordinal and non-normally distributed variables (such as the NIHSS) will be characterized by medians and interquartile ranges. Baseline characteristics will be compared between the tDCS stimulation group with sham group to assess covariate balance. Wilcoxon Rank-Sum tests will be used for continuous or ordinal variables; Fisher's exact tests and chi-square tests will be used for grouped or nominal categorical variables.

E.2.3. Safety and Tolerability (Specific Aim 1)

E.2.3.1 Dose Escalation

The study Data and Safety Monitoring Board (DSMB) will meet at the completion of each dose tier, review all safety data, and determine whether the study will proceed to the next dose tier. DSMB deliberations will be

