guided by: 1) a formal stopping/escalation rule, based on the occurrence of the lead safety endpoint, symptomatic intracranial hemorrhage (SICH), and 2) The DSMB members' clinical judgement upon review of all other safety outcomes. The formal dose escalation rule uses SICH frequency to gate the occurrence and pace of escalation through the 6 dose tiers. If no SICH occurs in the 3 active patients at a dose tier, enrollment may escalate to the next dose tier. If one SICH occurs, 3 more active (and 1 more control) patient will be enrolled at that dose tier before escalation. If 2 SICHs occur at a dose tier, further study enrollment is held until detailed review by the DSMB (Fig 6). In addition, whenever the formal SICH criteria for dose escalation has been met, the DSMB will formally meet, review the SICH data and all other safety data, and advice regarding proceeding to the next tier, continuing at the current tier, or placing the study on hold.

E.2.3.2. Primary Safety Endpoint Analysis

For the final statistical analysis of the primary SICH safety endpoint, a chi-square test will be used to detect differences in the rate of SICH between the active treatment and sham patients and higher and lower dose tiers. The treatment will be considered to have exhibited adequate safety in the current trial to proceed to future, larger, pivotal efficacy trials if tDCS results in lower or equivalent rates of SICH compared to sham.

E.2.3.3. Secondary Safety Endpoints Analysis

In secondary safety endpoint analyses, the following will be compared between the active treatment and sham patients, and between higher and lower dose tiers, using chi-squared tests: **1)** Asymptomatic ICH by 24h (intracranial hemorrhage not associated with NIHSS worsening ≥ 4); **2)** Early neurologic deterioration (worsening ≥ 4 on NIHSS during the 24-hour period after stimulation, with or without intracranial hemorrhage); **3)** All-cause mortality at day 90 (mRS); and **4)** All serious adverse events.

E.3.3. Tolerability Endpoint Analysis

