Clinical efficacy endpoints will be characterized in the active and sham patients, and in higher and lower dose tiers. Early course clinical efficacy endpoints of greatest interest that will be explored are: **1)** Normalized change in neurologic deficit from baseline to 24h (normalized delta NIHSS – linear variable, analyzed with means and 95% CIs; and **2)** Degree of neurologic deficit at 24h (NIHSS – quasi-linear variable, analyzed with means and 95% CIs). Final outcome clinical efficacy endpoints of greatest interest that will be explored are: **1)** Degree of disability at 90 days, assessed across all 7 levels of the modified Rankin Scale – ordinal variable, analyzed with medians (IQRs) and means (95% CIs); **2)** Functional independence (mRS 0-2) at 90 days – binary variable, analyzed with rates and 95% CIs; **3)** Granular degree of disability at 90 days (AMC Linear Disability Scale) –

linear variable, analyzed with means and 95% CIs; and **4) Health-related quality of life (EQ-5D)** – linear variable, analyzed with means and 95% CIs.

E.3.5.2. Exploratory Imaging Biomarker Efficacy Endpoints

This study is underpowered to definitively determine efficacy, so all imaging efficacy analyses will be purely exploratory and descriptive. The imaging efficacy analysis will be done on the subgroup of patients (including tier 5 and 6 patients who have presence of salvageable penumbra in their entry criteria) with baseline pre-EVT penumbral imaging demonstrating presence of salvageable penumbra with $T_{max} > 6$ sec/ ischemic core volume of ≥ 1.2 .

Imaging biomarker efficacy endpoints will be characterized in the active and sham patients, and in higher and lower dose tiers, using means and 95% confidence intervals. The six imaging efficacy endpoints of greatest interest that will be explored are: early and late penumbral salvage, early and late collateral flow enhancement, and early and late infarct growth.

References:

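### E.2.1's multiple-imputation rule makes no exception for death, so the exploratory day-90 AMC and EQ-5D summaries could fail to reflect deaths

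*Combined protocol and SAP*

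**What the plan says.** The missing-data rule stands at the end of E.2.1 (Sample size): "Should any missing data occur, primary analyses will be performed using multiple imputation", "with sensitivity analyses including complete case and worst possible outcome analyses". It specifies no imputation model and does not mention death.

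The scales concerned are set out in E.3.5.1, which labels all clinical efficacy analyses exploratory and descriptive:

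- **24-hour NIHSS:** the score at 24 hours and "Normalized change in neurologic deficit from baseline to 24h", both summarised by means and 95% CIs.
- **AMC Linear Disability Scale (day 90) and EQ-5D (collected at day 90):** means and 95% CIs.
- **Barthel Index:** named as an outcome measure and collected at day 90 (D.6.8), but absent from the list of endpoints with a stated analysis.
- **mRS at day 90:** "assessed across all 7 levels of the modified Rankin Scale", plus the proportion with mRS 0-2.

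No section gives a value for death on the NIHSS, AMC, EQ-5D or Barthel. The mRS differs: E.2.3.3 reads all-cause mortality at day 90 from it, so death has its own level there. That mortality endpoint is a secondary safety endpoint, compared between active and sham and between higher and lower dose tiers.

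**The concern.** A patient who has died has no quality-of-life or disability score to recover. The value does not exist, which is different from a value that exists but was not observed. Multiple imputation suits the second case. Applied to the first, it predicts what the dead patient would have scored had he or she behaved like the survivors with similar covariates.

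If the two arms differ in mortality, the imputed means compare something close to survivor with survivor. An arm with more deaths could then show the same mean EQ-5D or AMC score as the other arm, and an arm with fewer deaths would get no credit on those scales. The masking works in both directions.

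Adding the mRS to the imputation model would not help, since no patient with an observed AMC or EQ-5D score has the mRS level for death.

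These scales are named under Specific Aim III, and D.6.10.2 says that the decision on further development will weigh all outcome measures. A misleading summary could therefore be read and used.

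**Working it through.** **Plan's own figure.** The stated sample size reproduces: 6 tiers × (3 active + 1 sham) = 24, that is 18:6; 6 × (6 + 2) = 48, that is 36:12. No stated sample size or power depends on how deaths are scored.

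**Inputs that the documents do not give.** Death rates, score means and score spread are all assumed below. The survivor EQ-5D mean is taken as 0.70 in both arms (no effect in survivors), and death is scored 0.

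**Direct arithmetic at 18:6.** Mean with death scored 0 = 0.70 × (survivors / patients). Imputation at the survivor mean gives 0.70 − 0.70 = 0 in every row.

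| Deaths, active v sham | Active mean | Sham mean | Difference, death = 0 | Difference, imputed |
|---|---|---|---|---|
| 3/18 v 1/6 | 0.70 × 15/18 = 0.583 | 0.70 × 5/6 = 0.583 | 0 | 0 |
| 6/18 v 1/6 | 0.70 × 12/18 = 0.467 | 0.583 | −0.117 | 0 |
| 9/18 v 1/6 | 0.70 × 9/18 = 0.350 | 0.583 | −0.233 | 0 |
| 2/18 v 2/6 | 0.70 × 16/18 = 0.622 | 0.70 × 4/6 = 0.467 | +0.156 | 0 |

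The last row shows a survival advantage being lost in the same way.

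**Check with actual multiple imputation.** Copying the survivor mean is a simplification, so the comparison was simulated with a normal-regression imputation on arm and baseline NIHSS. Further assumptions: baseline NIHSS mean 16 and SD 6, score slope −0.015 per NIHSS point, residual SD 0.20, and risk of death rising with baseline NIHSS.

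| Nominal mortality, active v sham | Imputed difference, 18:6 / 36:12 | Death = 0 difference, 18:6 / 36:12 |
|---|---|---|
| 17% v 17% | 0.004 / 0.001 | −0.006 / 0.000 |
| 33% v 17% | −0.001 / 0.000 | −0.106 / −0.104 |
| 50% v 17% | 0.001 / −0.001 | −0.212 / −0.217 |

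Imputed scores for dead patients averaged 0.66 to 0.67, against 0.70 to 0.71 in survivors. Using a prognostic covariate lowers the imputed values only slightly.

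**Precision.** For 6/18 v 1/6 deaths, counting only the variation between 0 and 0.70, the variances are 0.49 × (1/3)(2/3) = 0.109 and 0.49 × (1/6)(5/6) = 0.068. The standard error is √(0.109/18 + 0.068/6) = 0.13, so the 95% CI half-width is about 1.96 × 0.13 = 0.26.

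**Power of the separate mortality comparison** (two-sided 0.05, an assumption; approximate): 33% v 17% gives 9% at 18:6 and 15% at 36:12; 50% v 17% gives 26% and 52%.

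**The case against.** A reader might infer that the trial would hide a mortality difference. The documents do not support that. Day-90 mortality is its own between-arm endpoint (Hypothesis I-b, E.2.3.3). Fatal events are recorded as serious adverse events for 90 days (D.6.10.1), and all serious adverse events are compared between arms. The DSMB reviews all safety data after each tier (E.1). Deaths enter the seven-level mRS and count as failures on mRS 0-2. Escalation and the adequate-safety criterion rest on SICH (E.2.3.1, E.2.3.2), not on these scales. All of this stands. The low power of the mortality comparison means that a real difference may not reach significance; it does not remove the deaths from view.

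It can also be said that E.2.1 never calls death missing data, that the preceding sentence concerns missed visits, and that its rule covers primary analyses while these scales are exploratory. That reading is possible. The wider one is likelier: the sentence covers any missing data and sets primary against sensitivity analyses, and the visit windows and travel to patients fit the day-90 assessments. If the narrow reading is right, the plan has no rule for deaths on these scales, and the same wording is needed.

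Finally, the sensitivity analyses already include worst possible outcome, which would partly expose the effect. That stands in part. Worst-outcome scoring also penalises living patients lost to follow-up, so it does not isolate death; complete case drops the dead. Neither is the leading summary.

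**Conclusion.** The point holds in a limited form. Followed literally, E.2.1 gives dead patients scores modelled on survivors, so the affected summaries would not reflect deaths. Chiefly this concerns AMC and EQ-5D at day 90. The 24-hour NIHSS is affected only by deaths before 24 hours; day-90 NIHSS is collected without a stated analysis; Barthel matters only if it is analysed.

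The size depends wholly on assumed inputs. On a scale with a survivor mean of 0.70 and death scored 0, the part not shown is 0 when mortality is equal, about 0.10 to 0.12 when it is roughly 33% v 17%, and about 0.21 to 0.23 at 50% v 17%. With a CI half-width of about 0.26 at 18:6, even the correctly scored difference of −0.12 would be imprecise. Severity is minor: the endpoints are exploratory and deaths are reported elsewhere.

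**What to change.** In E.2.1 and E.3.5.1, state that:

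1. multiple imputation is used only for patients known to be alive whose score was not obtained;
2. in the main summary, patients who die before the assessment take a prespecified death or worst value on each analysed scale, with the value named for AMC, EQ-5D, 24-hour NIHSS, and Barthel if an analysis is added;
3. a survivor-only summary, labelled as such, is shown beside the number of deaths in each arm.

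The documents give no convention for the values in item 2, so the sponsor must choose and justify them; the 0 used above is only an illustration.

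The cost is wording only, since vital status is already collected. The downside is more skewed distributions, so medians should be reported alongside the planned means and 95% CIs.

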Hypothesis I-a: C-tDCS will be safe in AIS patients receiving EVT with no increased risk of symptomatic intracranial hemorrhage (SICH) within the 24-hour period after EVT. Hypothesis I-b: C-tDCS will not increase the rates of asymptomatic intracranial hemorrhage, early neurological deterioration (NIHSS during the 24-hour period after stimulation), 90-day mortality, and all serious adverse events. Hypothesis I-c: Majority of AIS patients ($\geq 90\%$) will tolerate the C-tDCS by completing at least 75% of the stimulation period with no major stimulation related pain, discomfort and skin changes.

Specific Aim II: To determine the feasibility of delivering C-tDCS as an adjunct and bridge to EVT.

Hypothesis II-a: Adjunctive C-tDCS after endovascular thrombectomy will be started more rapidly after the end of ET procedure over the course of the study and in the last 10 patients, median time from end of ET procedure to C-tDCS initiation will be ≤ 10 minutes. Hypothesis II-b: Bridging C-tDCS prior to endovascular thrombectomy will be started more rapidly over the course of the study and in the last 4 patients, median time from randomization to C-tDCS initiation will be ≤ 10 minutes.

Specific Aim III: To explore the potential imaging and clinical efficacy of tDCS in AIS as an adjunct and bridge to EVT.

1) Early and late penumbral salvage, defined as proportion of penumbral tissue on baseline multimodal MRI that does not proceed to infarct on 2-hour and 24-hour MRI (PWI); 2) Early and late collateral enhancement, evidenced by reduced perfusion lesion volume on 2-hour and 24-hour perfusion-weighted MRI (PWI); 3) Early and late reduction in infarct growth from baseline to 2-hour and 24-hour MRI; 4) Early improvement in neurologic deficit (NIHSS at 24h); 5) Improvement in final 3-month disability and quality of life (modified Rankin scale, AMC Linear Disability Scale, EQ-5D, and Barthel Index)

Impact

This in-hospital safety trial, will identify C-tDCS dose regimens that are feasible, well-tolerated, and preliminarily safe in patients with acute ischemic stroke who undergo ET. Study finding will identify the most promising dose regimens to advance to phase 2b and pivotal phase 3 efficacy trials for three patient populations with pressing need for improved therapies: 1) thrombectomy-eligible patients arriving directly to thrombectomy-capable hospitals who would benefit from post-arrival brain protection; 2) thrombectomy-eligible patients arriving initially

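### The worst-outcome sensitivity analysis, on its plain reading, is not a conservative check for the no-excess-harm comparisons, and can reverse an observed excess when a larger share of sham than active data is missing

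*Combined protocol and SAP*

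**What the plan says.** Section E.2.1 sets one missing-data rule for the whole trial. For the main results, it says: "Should any missing data occur, primary analyses will be performed using multiple imputation". Supporting checks are then planned, "with sensitivity analyses including complete case and worst possible outcome analyses". It does not define the worst outcome by endpoint, and it does not say whether active and sham patients are scored the same way.

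The safety claims are all of the no-excess type. For SICH, E.2.3.2 states that "a chi-square test will be used to detect differences in the rate of SICH between the active treatment and sham patients", and safety is judged adequate for larger trials "if tDCS results in lower or equivalent rates of SICH compared to sham". No margin or confidence bound is given. Hypothesis I-b in Specific Aims says that "C-tDCS will not increase the rates of asymptomatic intracranial hemorrhage", and extends this to early neurological deterioration, 90-day mortality and all serious adverse events. E.2.3.3 compares those endpoints between arms without a pass threshold.

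The design is a 3+3 escalation "with 3:1 randomization to active treatment vs sham control". On size, E.2.1 says "The 3+3 study design (3 patients and 1 sham) with 6 dose tiers yields a sample size of at least 24 and potentially up to" a maximum of 48. On expansion, E.2.3.1 says: "If one SICH occurs, 3 more active (and 1 more control) patient will be enrolled at that dose tier before escalation".

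**The concern.** Giving every missing patient the bad outcome is usually regarded as cautious when the aim is to show that a treatment is better. Here the aim is to show that it is not worse. An event assigned to a missing sham patient raises the comparator rate and makes the criterion easier to meet. With three active patients per sham patient, one such event moves the sham rate three times as far as one imputed active event moves the active rate.

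What is at stake is how the result is read. Agreement with an analysis bearing this label would be taken as evidence that missing data do not conceal harm. In a first-in-human acute stroke trial with 6 to 12 sham patients, it may show no such thing.

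**Working it through.** **Sample size.** Six tiers of 3 active + 1 sham give 6 × 4 = 24. If every tier is expanded, 6 × (6 + 2) = 48. Both match E.2.1. The arms are therefore 18/6 at the minimum and 36/12 at the maximum. One expanded tier gives 5 × 3 + 6 = 21 active and 5 × 1 + 2 = 7 sham. Three expanded tiers give 3 × 3 + 3 × 6 = 27 active and 3 × 1 + 3 × 2 = 9 sham.

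**Criterion.** I read E.2.3.2 as: pass if the active proportion is less than or equal to the sham proportion.

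**Weight of one imputed event.** Sham: 1/6 to 1/12, or 16.7 to 8.3 percentage points. Active: 1/18 to 1/36, or 5.6 to 2.8 points. The ratio is 3.

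**General condition.** Let p be the complete-case rate and m the missing share in an arm. If every missing patient gets the event, the rate becomes p(1 − m) + m, so the event-free proportion is (1 − p)(1 − m). The criterion is then met when (1 − pA)(1 − mA) ≥ (1 − pS)(1 − mS). If complete cases fail (pA > pS), this can hold only when mS > mA. That condition is necessary but not sufficient. If mA = mS = m, the difference becomes (1 − m)(pA − pS): smaller, with the same sign.

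**Cases that the escalation rule can produce** (active vs sham; missing patients are not replaced):

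| Arms | SICHs observed | Missing | Complete case | Event to all missing | Event to missing active only |
|---|---|---|---|---|---|
| 21/7 | 1 active | 1 sham | 1/21 (4.8%) vs 0/6: fail | 1/21 (4.8%) vs 1/7 (14.3%): pass | 1/21 vs 0/7: fail |
| 27/9 | 3 active, in three tiers | 1 sham | 3/27 (11.1%) vs 0/8: fail | 3/27 vs 1/9 (both 11.1%): pass | 3/27 vs 0/9: fail |
| 21/7 | 1 active | 1 active, 1 sham | 1/20 (5.0%) vs 0/6: fail | 2/21 (9.5%) vs 1/7 (14.3%): pass | 2/21 vs 0/7: fail |
| 21/7 | 1 active | 3 active, 1 sham (equal shares) | 1/18 (5.6%) vs 0/6: fail | 4/21 (19.0%) vs 1/7 (14.3%): fail | 4/21 vs 0/7: fail |
| 18/6 | none | 1 active | 0/17 vs 0/6: pass | 1/18 (5.6%) vs 0/6: fail | 1/18 vs 0/6: fail |

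In the fourth row the difference shrinks from 5.6 to 4.8 points, which is 5.6 × (1 − 1/7), and the verdict stands. In the fifth row the rule counts against C-tDCS.

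**Assignment least favourable to C-tDCS.** With missing active = event and missing sham = no event, the active rate cannot fall and the sham rate cannot rise, so a complete-case fail can never become a pass. Exact enumeration at 18/6 and 36/12, for combinations of up to 6 missing active and 2 missing sham patients, found no such change.

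**Day-90 mortality, illustration.** Deaths do not trigger tier expansion, so 18/6 is a possible size. Assume 4 active deaths, 1 sham death and one sham patient lost; these counts are mine, not the protocol's. Complete cases give 4/18 (22.2%) vs 1/5 (20.0%), 2.2 points higher on active. Counting the lost patient as dead gives 22.2% vs 2/6 (33.3%), 11.1 points lower. Counting that patient as alive gives 22.2% vs 1/6 (16.7%), 5.6 points higher.

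**The case against.** Several points on the other side stand.

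- E.2.1 never says that missing sham patients receive the event. That is the natural meaning of the phrase, but it is an inference. If it is rejected, the rule is undefined and the same clarification is needed.
- A reader might infer that the analysis generally makes C-tDCS look safer. The documents and the algebra do not support this. If dropout is equally likely in both arms, about three active patients are missing for each sham patient, which offsets the threefold weight.
- A reader might infer larger reversals, such as 2/18 or 6/18 active SICHs passing against a sham arm of 6, or 3/36 against 12. These do not fit the escalation rule. Two SICHs with no expansion must fall in one cohort of three, which holds enrolment for DSMB review; 6/18 would need at least two such cohorts. Reaching 36/12 under the formal rule takes a SICH in each of six tiers, so at least six active SICHs.
- SICH is a 24-hour endpoint in patients under intensive monitoring, with protocol imaging and NIHSS at 2 and 24 hours (section D.4 on adjunctive stimulation). Missing values should be rare. Asymptomatic haemorrhage and early deterioration share that window.
- Multiple imputation is primary, complete-case results are shown alongside, and no decision rule is attached to the sensitivity analyses. D.6.10.2 rests the decision to proceed on all outcome measures together.
- The fragility comes largely from a criterion without a margin and a very small sham arm, which a different imputation rule does not cure.

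These points limit the size of the problem. They do not make the analysis a conservative one. Because D.6.10.2 calls for an overall assessment, the sensitivity results will be read. E.2.1 also plans for missed follow-up by offering to travel to patients.

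**Conclusion.** The point holds in a limited form. Read plainly, the worst-outcome analysis is not conservative for the active-versus-sham safety comparisons. When a larger share of sham than active patients is missing, it can reverse an observed excess of harm, and one missing sham patient is enough (1/21 vs 0/6 becoming 1/21 vs 1/7). With equal missing shares it only dilutes the difference. With only active patients missing, it is stricter on C-tDCS.

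A reader might go further and conclude that the trial's safety verdict would be overturned. The documents do not support that: the formal criterion covers SICH only, the primary analysis is multiple imputation, and the reversal appears in a sensitivity table. The practical exposure is mainly day-90 mortality and 90-day serious adverse events. These have no pass threshold, so there the effect is on the direction of the reported difference, by 8.3 to 16.7 points of sham rate per missing sham patient at 12 and 6 sham patients.

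The conclusion assumes that both arms are scored alike, that the criterion compares observed proportions, and that missing patients are not replaced. The protocol gives no expected rate of missing data, so how often a reversal would occur cannot be stated.

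**What to change.** In E.2.1, define the worst-case analysis by endpoint and arm. For SICH and the E.2.3.3 safety endpoints:

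1. Add an analysis least favourable to C-tDCS: missing active = event, missing sham = no event.
2. Report the reverse assignment as the other bound, or give a tipping-point table over all combinations of imputed events.
3. State that the safety conclusion will be read against both bounds.

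The general worst-outcome analysis may stay for the other endpoints.

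The cost is a sentence in E.2.1 and a few simple tables. The downside is that the sensitivity result can be less favourable to C-tDCS, and the bounds may be wide with 6 to 12 sham patients. In the 21/7 case with three active and one sham missing, they run from 4/21 vs 0/7 (19.0 points higher on active) to 1/21 vs 1/7 (9.5 points lower). That width reflects how little the data can say when outcomes are missing.

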Tier 6 - 2 mA, in 3 treatment cycles. First cycle will be a 20 min cycle, administered after initial imaging either in the Roland Reagan Medical Center or mobile stroke unit and prior to arterial puncture (cycle will be shorter than 20 minutes if EVT puncture is ready to proceed, in order not to delay EVT). The second cycle will start at the conclusion of the EVT procedure in patients with TICI<2c and 3 and negative immediate post-EVT CT scan for a definitive evidence of ICH (and not sooner than 20 minutes after the end of the first cycle), and will last 20 minutes. The third cycle will start 20 minutes after the end of the second cycle, and will last 20 minutes.

Patients in the sham stimulation arm at all the tiers will have the cap and electrodes in place, but without any delivered electrical stimulation. While the highest dose tier in this study is expected to be fully safe, based on preclinical and clinical studies ^{11,18}, since this is a first-in-human study in acute stroke, a formal escalation to higher dose tiers is prudent.

[figure not shown]

Figure 7. This figure shows the 6 escalating tiers. Blue represents 1 mA, purple shows 2 mA of C-tDCS. The black/white neuroangi suite icon represents the endovascular thrombectomy (EVT) procedure, occurring before the adjunctive C-tDCS at all tiers if EVT results in a less than a complete recanalization (TICI <2c, 3). At tiers 5 and 6, bridging C-tDCS occurs for up to 20' before EVT. Symptomatic ICH (SICH) in none of the three C-tDCS patients in a tier will result in escalation. However, if SICH occurs in one C-tDCS patient, 3 more C-tDCS patients and 1 more sham will be enrolled at the same tier.

D.4. Management pre, during, and post adjunctive stimulation period

As soon as the endovascular thrombectomy (EVT) ends, a CT head will be obtained in patients with less than a complete EVT reperfusion (TICI < 2c,3) and if negative for definitive evidence of intracranial hemorrhage, then the patient will be randomized, and the adjunct stimulation will be initiated in neurosurgical intensive care unit according to the tier that patient is assigned to.

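### A trial that clears all six tiers by the 3+3 rule cannot give a significant SICH chi-square for harm, and its active SICH rate is conditional on having passed that gate

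*Combined protocol and SAP*

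**What the plan says.** Section E.2.1 sets six tiers of 3 active and 1 sham patients, which "yields a sample size of at least 24 and potentially up to 48". Section E.2.3.1 makes enrollment depend on the outcome. A tier whose first three active patients are all free of SICH can be followed by the next one. For a single event the rule reads: "If one SICH occurs, 3 more active (and 1 more control) patient will be enrolled at that dose tier before escalation". Two SICHs at a tier hold enrollment until the DSMB has reviewed the case. The Figure 7 legend ties expansion to the active arm: "if SICH occurs in one C-tDCS patient, 3 more C-tDCS patients and 1 more sham will be enrolled at the same tier". The two-SICH sentence in E.2.3.1 does not say which arm counts.

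Section E.2.3.2 then specifies that "a chi-square test will be used to detect differences in the rate of SICH between the active treatment and sham patients", with the same test for higher against lower tiers. The treatment is judged safe enough for larger trials "if tDCS results in lower or equivalent rates of SICH compared to sham". The plan gives no significance level, margin or interval for SICH, and no adjustment for the escalation rule.

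**The concern.** A chi-square test treats the counts as coming from samples of fixed size. Here the number of active patients, and whether the trial continues, depend on the active SICH count. Among tiers cleared by rule, the active count is capped. On the Figure 7 reading, sham SICH triggers nothing.

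If all six tiers clear, a non-significant test could be taken as evidence of no harm when significance for harm was not attainable. The active rate compared with sham would also come from a trial selected for having few active events. Both feed the statement on whether to go on to larger trials.

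**Working it through.** **Inputs.** From the plan: six tiers, cohorts of 3 active and 1 sham, and expansion by 3 and 1 (E.2.1, E.2.3.1, Figure 7 legend). Assumed because the plan does not give them: two-sided 5% for the SICH test; true SICH rates of 5%, 10% and 20% active and 5% or 10% sham; equal risk at every tier. For the bias and probability figures, a hold is treated as the end of the trial.

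**1. The plan's own figure.** 6 × (3 + 1) = 24 and 6 × (6 + 2) = 48. Both match.

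**2. The cap.** A tier clears by rule at 0/3 or 1/6 active SICH. With k expanded tiers, a rule-cleared trial has k SICH in 18 + 3k active patients and has 6 + k sham patients.

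**3. Strongest evidence of harm (no sham events).** Pearson chi-square without continuity correction is N(ad − bc)² divided by the product of the four margins. For k = 6: 48 × (6 × 12 − 30 × 0)² / (36 × 12 × 6 × 42) = 248,832 / 108,864 = 2.286, p = 0.131 (one-sided 0.065; Fisher 0.315).

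| k | Active | Sham | p |
|---|---|---|---|
| 1 | 1/21 | 0/7 | 0.56 |
| 2 | 2/24 | 0/8 | 0.40 |
| 3 | 3/27 | 0/9 | 0.30 |
| 4 | 4/30 | 0/10 | 0.22 |
| 5 | 5/33 | 0/11 | 0.17 |
| 6 | 6/36 | 0/12 | 0.13 |

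For higher against lower tiers in active patients, the smallest p over all consecutive cuts is 0.105 (1/6 in tier 6 against 0/15 below it: 21 × 15² / (6 × 15 × 1 × 20) = 2.625).

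**4. Released holds.** An expanded tier can reach 1 + 3 = 4 SICH in 6. If the DSMB releases one such hold and the trial moves to the next tier, the extreme is 5 + 4 = 9/36 against 0/12, p = 0.055. Two releases give 4 + 8 = 12/36 against 0/12, p = 0.021. This counts a release as moving on. E.2.3.1 also lets the DSMB advise continuing at the same tier; a tier at 3/3 that then took three more patients could reach 6/6, so 11/36 against 0/12: 48 × (11 × 12)² / (36 × 12 × 11 × 37) = 4.76, p = 0.029.

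**5. The other direction.** On the Figure 7 reading, 0/18 against 2/6 gives 24 × (18 × 2)² / (18 × 6 × 2 × 22) = 6.545, p = 0.011. Significance in favour of stimulation is reachable.

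**6. Bias.** With p the true rate and q = 1 − p, a tier clears with probability q³ + 3pq⁵. At p = 0.10 this is 0.729 + 0.177 = 0.906, so all six clear with probability 0.906⁶ ≈ 0.55. A cleared tier was expanded with probability e = 0.177 / 0.906 = 0.195. Averaging k/(18 + 3k) over a binomial k (6 tiers, probability e) gives 5.0%.

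| True active rate | P(all six clear) | Mean rate if completed | Mean rate, all trials |
|---|---|---|---|
| 5% | 85% | 3.2% | 6.0% |
| 10% | 55% | 5.0% | 13.6% |
| 20% | 13% | 6.7% | 27.9% |

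These are means of the per-trial rate.

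**7. The raw-rate criterion.** In completed trials the active rate exceeds sham with probability 0.37 (true rates 5% v 5%), 0.50 (10% v 5%) and 0.59 (20% v 5%).

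**8. The same test without the gate.** Exact power for harm at 10% v 5% is 0.01% with 18:6 patients and 0.12% with 36:12. At 20% v 5% it is 1.2% and 9.3%.

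**The case against.** The best defence is that the gate, not the final test, is meant to catch harm. At a true 20% active rate, 87% of trials meet a hold before clearing six tiers. The DSMB reviews all safety data at each tier, and D.6.10.2 says the decision on further development will weigh all outcome measures. The sample is also so small that an ungated chi-square would almost never detect harm at plausible rates. All of this stands, and it limits the severity. It does not make the planned test informative: an ungated trial could in principle reach significance (8/18 v 0/6, p = 0.046; 10/36 v 0/12, p = 0.040), whereas one cleared by rule cannot.

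A reader might infer that the gate makes a harmful treatment more likely to be declared safe. The figures do not support that. At 10% v 5%, active is no higher than sham in 50% of completed trials, but in 35.3% of all gated trials, against 35.2% in a fixed 18:6 trial. The chance of both completing and showing active no higher than sham is 27.8%. At 20% v 5% that chance is 5.2%, against 16.1% in the fixed trial. The tilt arises from looking only at completed trials.

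**Conclusion.** The point holds for trials that clear all six tiers by rule. Such a trial cannot give a significant chi-square for harm at an assumed two-sided 5% level: the smallest p is 0.131 for active against sham. If a released hold means moving to the next tier, one release reaches p = 0.055 at best and two are needed to go below 0.05. The limit on harm holds whichever arm's SICH counts, since active SICH stays at or below 1/6 per cleared tier. The reachable result in favour of stimulation at 0/18 v 2/6 depends on the Figure 7 reading.

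Two broader readings go too far. One is that no completed trial can show harm. The stated criterion compares rates, and a completed trial can fail it; released holds can also lift the cap. The other is that the active rate is simply biased low. That is so given completion; over all trials the mean is biased high.

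The small sample is an independent cause of the lack of power. The true rates and the 5% level are assumptions, because the plan states none. This should be fixed.

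**What to change.** In E.2.3.2:

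- Stop using the SICH chi-square tests as the basis for a safety conclusion. Call the active–sham and tier comparisons descriptive.
- Report the SICH rate in all treated active patients, including any held tier, with an ordinary exact one-sided 95% upper bound. For a rule-cleared trial with 0 to 6 expanded tiers the bounds are 15.3%, 20.7%, 24.0%, 26.3%, 28.0%, 29.3% and 30.3%. Show the sham rate beside it with an exact interval.
- State that a tier cleared by rule cannot show more than 1/6 active SICH, that a completed trial's active rate is conditional on passing the gate, and that meeting the criterion "if tDCS results in lower or equivalent rates of SICH compared to sham" is not by itself evidence of safety.
- If a p value is kept, take its reference distribution from the full 3+3 rule, holds included.
- Reconcile the two-SICH sentence in E.2.3.1 with the Figure 7 legend on which arm counts.

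The ordinary bound ignores the gate, but it also works for held trials. With two or more expanded tiers it is more cautious than a bound computed from the 3+3 paths (24.0% to 30.3% against 23.4% to 24.7%); with one it is nearly the same (20.7% against 20.8%).

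The cost is a less favourable safety statement and a little more analysis work.
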